13.3 Analysis Populations

13.3.1 Safety Population

The *safety population* consists of all subjects who receive any amount of study medication. All data summaries except PK-data related summaries will use this population.

13.3.2 Pharmacodynamic Population

The *pharmacodynamic population* includes those subjects in the safety population who have at least one measurable post-IP exposure sample for a PD parameter.

13.3.3 Efficacy Population

Subjects in the safety population who have at least 1 posttreatment assessment for a marker of clinical activity will be included in the efficacy population.

13.4 Subject Disposition

Subject disposition data will be summarized and will include the number and percent of enrolled subjects; number and percent of subjects initiating and completing treatment; and number and percent of subjects discontinuing treatment and discontinuing the study, further broken down by the reasons for discontinuation. Subject enrollment will also be summarized by study site. A summary of major protocol deviations will be tabulated for each cohort and cohorts combined by treatment group.

13.5 Demographics and Baseline Characteristics

Demographics and other baseline characteristics will be summarized for the subjects in the safety population. Demographic data will include age, gender, race, and ethnicity.

13.6 Safety Analyses

All safety data summaries will use the safety population.

The number and percent of subjects experiencing any DLTs will be presented by cohort. A listing of DLTs will also be provided.

Adverse events (including DLTs) will be coded using MedDRA (v 20.1, or the current version) and will be graded by the investigator using the NCI CTCAE v 5.0 or the current version. Subject incidence of TEAEs, TESAEs, TEAEs leading to treatment discontinuation, AESIs, and TEAEs with an outcome of death will be summarized by SOC and preferred term. Adverse events will also be further summarized by worst CTCAE severity grade and relationship to study drug. In addition, AESIs as described in Section [Error! Reference source not found.](#) will also be summarized by SOC, preferred term, and worst severity grade.

Clinical laboratory data will be summarized descriptively, and the summaries will include observed values at collection time points and their changes from baseline. All laboratory parameters that can be graded using the CTCAE v 5.0 will be graded. For selected parameters, the following summaries may be produced:

- Worst postbaseline severity grade
- Shift summary of baseline grade to worst postbaseline severity grade.

Safety evaluations may also include changes in the subject's vital signs and ECG findings.

13.7 Pharmacodynamic Analyses

All PD data summaries will use the PD population.

Detailed PD analyses are outlined in [Appendix C Mechanistic Assessments](#).

13.8 Efficacy Analyses

Data will be summarized descriptively by treatment arm and overall. The descriptive summary for the categorical variables will include counts and percentages. Chi-squared tests (or Fisher's exact tests, as appropriate) will be used to compare categorical variables between study arms. Descriptive summaries for the continuous variables will include means, medians, standard deviations and minimum and maximum values. Two-sample t-tests (or Wilcoxon rank-sum tests, as appropriate) will be used to compare continuous variables between the two study arms. Time to recovery will be summarized using the Kaplan-Meier method and compared between study arms using the log-rank test.

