8.6.3 Secondary Efficacy Endpoints

Part 2 (Phase 2a):

Efficacy of cePolyTregs compared with placebo/SOC, as assessed by:

- The proportion of subjects with a 2-point or greater improvement in the WHO severity scale for COVID-19 pulmonary syndrome on each of Study Days 7, 14, 21, and 28
- The proportion of subjects with improvement in the WHO severity scale for COVID-19 pulmonary syndrome to Grade 3 or less on each of Study Days 7, 14, 21, and 28
- The proportion of subjects requiring mechanical ventilation on each of Study Days 7, 14, 21 and 28
- Number of days free of mechanical ventilation on Days 29 and 57
- Mean and median Sequential Organ Failure [SOFA] scores on each of Study Days 7, 14, 21 and 28
- Change in chest imaging (radiograph or CT scan) abnormalities
- All-cause mortality on Study Days 29 and 84

Parts 1 and 2:

Pharmacodynamic and biomarker changes associated with administration of cePolyTregs compared with placebo/SOC, including but not limited to:

- Change from baseline in circulating cePolyTregs
- Change from baseline in pulmonary cePolyTregs by endotracheal aspirate and mini BAL

UCSF	Clinical Study Protocol No. UCSF-cePolyTregs-01	Page 35 of 72
------	---	---------------

- Change from baseline in ferritin, C-reactive protein, LDH, and high-sensitivity troponin I (hs-TnI)
- Change from baseline in d-dimer
- Change from baseline in absolute lymphocyte count
- Change from baseline in C3, C4, and CH50
- Change from baseline in inflammatory cytokines/chemokines, e.g. IL-6, IL-12, IFN γ , TNF α , MCP-1 and MCP-4
- Phenotypic and functional changes from baseline in immune subsets using cytometric, genomic and/or proteomic analyses of cells harvested from endotracheal tubes, mini BAL, and blood

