10.2 Packaging and Labeling

cePolyTregs are cryopreserved in either CryoMACS[®] Freezing Bag 50 or CryoMACS[®] Freezing Bag 250 depending on the dose. The CryoMACS[®] Freezing Bag consists of a freezing bag and corresponding overwrap bag. Both the freezing bag and overwrap bags are composed of ethylene vinyl acetate tubular film and are individually packed and sterilized.

cePolyTregs are distributed to clinical study sites and stored in liquid nitrogen until use.

cePolyTregs will be labeled by the manufacturing site with product information including: product name and identifiers, method of manipulation, formulation, source cell material details,

date of cryopreservation, storage instructions, and all applicable statements and warnings. Product will be issued to each subject by the clinical site prior to infusion.

LHTR-CNNN - XXX-BB
Source cells Collection Facility:
Full Facility Name, Street Address,
City, State ZIP
Collection end date/Time/Time
Zone
DD-MMM-YYYY HH:MM ie.PT
Donor Number: #####

WARNING: Advise Patient of
Communicable Disease Risks
WARNING: Reactive Test Results for
CMV [if applicable]
Caution: New Drug – Limited by
Federal Law to Investigational Use

DO NOT IRRADIATE
DO NOT USE LEUKOREDUCTION
FILTERS
Store below -130°C 

**Cryopreserved Ex Vivo Expanded
Polyclonal CD4⁺CD127^{lo}/CD25⁺ T
Regulatory Cells**

Contains XXX x10⁶ cells in ## mL of
CryoStor[®] CS5

Cryopreserved on DD-MMM-YYYY

Method of manipulation: [12 or
13] day Ex Vivo polyclonal
expansion using anti-CD3/anti-
CD28 expansion beads and IL-2.
Manufactured and Processed by
UCSF HICTF and GMP Facility
[name],
94103, USA
FDA Registration # FEI3005404215

As is generally the case with blood products and cellular therapies, the labels on the cePolyTregs bags and the placebo bags will be different and will need to be checked at bedside as part of the infusion process. Consequently, study product identity will be blinded for the subjects and investigators but will not be blinded for other site staff.

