10.3 Study Drug Dosage Preparation

cePolyTregs will be kept in a monitored freezer in vapor phase liquid nitrogen (LN₂) until the time of infusion. Stability after thawing is 4 hours. The long-term stability of cePolyTregs in LN₂ freezers is provided in the current Investigator's Brochure.

cePolyTregs will be prepared and administered under sterile conditions according to the Cell Therapy Manual. The cells will be thawed at the bedside using a water bath or comparable device maintained at 34°C to 38°C by trained personnel. There should be no frozen clumps left in the container at the time it is infused. If the cePolyTregs cell product appears to be damaged or the bag appears to be compromised, it should not be infused, and the site should notify HICTF and the GMP facility immediately.

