13.1 General Considerations

Part 1 (Phase 1)

Analyses for the primary safety endpoint will be descriptive. AEs will be classified using MedDRA version 20.0 or higher. The severity of the toxicities will be graded according to the NCI CTCAE version 5.0.

Part 2 (Phase 2a)

In the randomized, Phase 2 portion of the study, the primary efficacy endpoint is time to recovery, defined as the first day during the 28 days after randomization on which a subject meets the criteria for category 0, 1, 2, 3, or 4 on the WHO severity scale for COVID-19 pulmonary syndrome. The intent-to-treat (ITT) analysis will be carried out for the primary efficacy endpoint. Subjects will be analyzed according to the assigned treatment group, regardless of whether the subjects receive any study treatment or receive a different study treatment from that to which they were randomized. The primary analysis will be a stratified log-rank test of time to recovery with cePolyTregs compared with placebo/SOC, with stratification by WHO severity scale for COVID-19 pulmonary syndrome at enrollment. The test will be performed with a two-sided type I error rate of 10%. Data for subjects who fail to recover or die will be censored at Day 29.

Analysis of the primary safety endpoint will be descriptive according to the intervention received and no formal comparisons between the 2 study arms will be performed. The safety analysis set will consist of all subjects who received at least 1 dose of study drug. AEs will be summarized by dose cohort using numbers and proportions.

The assessment of PD and biomarker data are described in [Appendix C Mechanistic Assessments](#).

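### Secondary efficacy has no all-randomized analysis set, and sections 10.7 and 13.8 omit the WHO-score stratification that 13.1 and 13.2 require

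*Combined protocol and SAP*

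**What the plan says.** **Primary analysis.** Section 13.1 (and the synopsis) is clear: "The intent-to-treat (ITT) analysis will be carried out for the primary efficacy endpoint", by assigned arm whether or not treatment was given. The test is also named: "The primary analysis will be a stratified log-rank test of time to recovery with cePolyTregs compared with placebo/SOC", with WHO score at enrollment as the stratum.

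**Analysis sets.** Section 13.3 defines three populations, and all of them require study drug. Of the safety population, 13.3.1 says: "All data summaries except PK-data related summaries will use this population". The efficacy population in 13.3.3 is narrower still: "Subjects in the safety population who have at least 1 posttreatment assessment for a marker of clinical activity". The secondary efficacy endpoints in 8.6.3 include ventilation outcomes and "All-cause mortality on Study Days 29 and 84"; no section gives them an all-randomized set.

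**Randomization strata.** The synopsis (Study Design and Sample Size), 8.1.2 and 13.2 name study site and baseline WHO score. Section 10.7, which describes how the system operates, names study site only.

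**Tests.** For time to recovery, 13.8 says: "Time to recovery will be summarized using the Kaplan-Meier method and compared between study arms using the log-rank test". The synopsis paragraph on efficacy analyses says the same. Both name unadjusted chi-squared or Fisher tests and t or Wilcoxon tests for other outcomes.

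**Replacement.** Section 10.7 allows randomized but untreated subjects to be replaced. Sections 8.1.5 and 8.8.5, neither limited to Part 1, allow replacement of some early terminations. None of the three says whether the replaced subject stays in the analysis.

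A separate SAP is promised before database lock (synopsis; section 13). It is not in the file.

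**The concern.** The ITT rule is stated for one endpoint only. If 13.3 is followed for the rest, mortality and ventilation are compared among infused subjects while time to recovery is compared among all randomized subjects.

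Non-infusion need not be balanced between arms. The only instruction in the documents to withhold an infusion concerns the active product: "If the cePolyTregs cell product appears to be damaged or the bag appears to be compromised, it should not be infused". In addition, "study product identity will be blinded for the subjects and investigators but will not be blinded for other site staff". A treated-only mortality comparison could therefore lose the protection of randomization that the primary endpoint keeps.

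The two stratification gaps are separate. Section 10.7 conflicts with 13.2 on how subjects are randomized; 13.8 is looser than 13.1 on how they are analyzed. If the randomization system is built from 10.7 or the programs from 13.8, the trial departs from its own design. Randomization cannot be corrected afterwards.

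**Working it through.** **1. The plan's own power figure.** From 13.2: 67/252 recovered by day 14 on placebo, medians 31.4 and 16 days, 50 per arm, two-sided alpha 10%.

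- Placebo median: 14 × ln 2 / −ln(1 − 67/252) = 31.4 days.
- 28-day recovery: 1 − 2^(−28/31.4) = 46.1% and 1 − 2^(−28/16) = 70.3% (plan: 70.2%).
- Recovery hazard ratio: 31.4/16 = 1.9625. Expected recoveries: 50 × 0.461 + 50 × 0.703 = 58.2.
- Schoenfeld: (√58.2 / 2) × ln 1.9625 − 1.645 = 0.93, so power is 82.3%. Simulation of the unstratified test gives 81.7%.

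The stated 80% is reproduced to within about 2 points.

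**2. Who is left out of 13.3.** A subject who is randomized but never infused is outside the safety population and therefore outside the PD and efficacy populations, which are subsets of it. Section 10.7 expects such subjects, since it allows for their replacement. Section 13.1 keeps them for the primary endpoint only.

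**3. Size of the treated-only problem.** This is an illustrative worst case: no treatment effect, the 50% mortality anticipated in 8.8.6, and uninfused active subjects who die.

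- All randomized: 25/50 = 50.0%.
- One such subject left out: 24/49 = 49.0%.
- Two left out: 23/48 = 47.9%.

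If the omitted subject survives, the shift is the other way: 25/49 = 51.0%.

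**4. Size of the stratification mismatches.** Entry requires mechanical ventilation, so the baseline scores are 6 and 7. The documents give neither their mix nor their effect on recovery; both are assumed here. The simulation uses 50 per arm, exponential times in whole days, censoring at Day 29, overall placebo 28-day recovery fixed at 46.1% and hazard ratio 1.9625. There were 20,000 runs for power (standard error 0.3 points) and 40,000 for type I error (0.15 points).

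Power of the log-rank test, unstratified / stratified (%):

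| WHO 7 share | Hazard difference, 6 vs 7 | Randomized with WHO score | Randomized without WHO score |
|---|---|---|---|
| 30% | 1.5-fold | 81.3 / 81.8 | 81.7 / 82.0 |
| 30% | 2-fold | 79.5 / 81.2 | 79.4 / 81.3 |
| 30% | 3-fold | 78.0 / 81.8 | 75.8 / 81.1 |
| 50% | 1.5-fold | 81.1 / 81.6 | 81.0 / 81.6 |
| 50% | 2-fold | 79.6 / 81.6 | 78.7 / 81.1 |
| 50% | 3-fold | 74.6 / 80.5 | 73.1 / 80.6 |

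- The stratified test has 80.5–82.0% power under either randomization, so the 10.7 gap costs the primary analysis little.
- Dropping the strata from the test after WHO-stratified randomization costs 0.5 points at 1.5-fold, 1.7–2.0 at 2-fold and 3.8–5.9 at 3-fold.
- Type I error of the unstratified test after WHO-stratified randomization is 9.2–9.6% at 2-fold and 7.9–8.3% at 3-fold, against 10%. It is conservative.

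**5. Secondary proportions.** With 28-day recovery as a stand-in, a 50% WHO 7 share and WHO-stratified randomization, plain chi-squared against a WHO-stratified Cochran–Mantel–Haenszel test has power 75.6% vs 78.1% at 2-fold and 69.4% vs 75.7% at 3-fold.

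**The case against.** The strongest case on the other side has five parts.

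- **The primary endpoint is already protected.** Section 13.1 keeps untreated, and so replaced, subjects in the primary analysis, and its specific stratified test governs the general sentence in 13.8. This stands. What is left open on replacement concerns secondary endpoints, and 13.8 needs matching wording only.
- **The treated-only reading is inferred.** Section 13.8 names no population, and the sweeping line in 13.3.1 cannot be literal, because it conflicts with ITT in 13.1 and the PD population in 13.7. This stands in part. However, 13.3.3 does define an efficacy population, it is treated-only, and no alternative is offered.
- **Arm-dependent non-treatment is not shown.** A damaged bag does not mean the subject goes untreated. Placebo handling sits in a manual outside the file, investigators are blinded, and randomization and infusion both fall on Day 0. No non-treatment rate is given. This stands: imbalance is possible, not demonstrated. The mortality illustration also takes one direction and ignores replacement.
- **The severity effects are assumed.** This is correct. At 3-fold with a 50% WHO 7 share, modeled 28-day recovery on active is about 67%, below the planned 70.2%, so that row is not the design effect.
- **The SAP can settle it.** It could settle the analysis set, the tests and the handling of replaced subjects, but for the set it would have to override 13.3. It cannot repair a randomization already run with the wrong strata.

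**Conclusion.** The point holds and should be corrected. Secondary efficacy, including mortality, has no all-randomized set; that is the substantive gap. Section 10.7 contradicts four statements elsewhere on the randomization strata, and 13.8 and the synopsis efficacy paragraph are looser than 13.1 on the test.

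The effects are modest. The treated-only set can move apparent active mortality by about 1 point per omitted death. The unstratified log-rank test loses about 0.5 to 6 points of power over the assumed range, with type I error below nominal. The unadjusted secondary tests are valid, only less efficient. The primary analysis as written in 13.1, the sample size and the stated power are not in question. Power and type I figures beyond the plan's own rest on the assumed WHO 6/7 mix and hazard differences.

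**What to change.** 1. In 13.3, define ITT as all randomized subjects, analyzed as assigned, and use it for every Part 2 efficacy analysis. Limit the catch-all line in 13.3.1 to safety and baseline summaries.
2. State that any replaced Part 2 subject remains in ITT. Replacement itself can stay.
3. Add baseline WHO score to 10.7, and check before Part 2 that the randomization system carries it.
4. In 13.8 and the synopsis efficacy paragraph, specify the log-rank test as stratified by baseline WHO score.
5. Lower priority: stratify the secondary tests of proportions by WHO score and adjust SOFA for its baseline value, which is already collected at screening.

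**Cost.** Wording and one system check, with no new data or subjects. ITT brings dilution. If 5% or 10% of active subjects go untreated and respond like controls (an assumption; 2-fold, 50% WHO 7), stratified log-rank power falls from 81.6% to 77.9% or 73.6%; the primary analysis already accepts this. For a 28-day proportion, the 5% case takes the stratified test from about 78% to 74%. Up to 12 sites by 2 scores gives 24 cells of about 100/24 = 4.2 subjects, so some blocks will be incomplete.

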14 ADMINISTRATIVE CONSIDERATIONS

14.1 Investigator Responsibilities

The investigator is responsible for complying with all regulatory requirements relating to performing clinical research with an investigational product. The investigator is responsible for ensuring that the investigation is conducted according to the signed Investigator Agreement (FDA Form 1572, or equivalent), the approved protocol, and applicable regulations for protecting the rights, safety, and welfare of study subject under the investigator's care. The investigator is additionally responsible for the control of investigational product and for providing accurate and verifiable data to the Sponsor.

The investigator must obtain the written informed consent of each subject before participation in the study. The investigator must assure initial and continuing review of the study by an IRB that complies with applicable national and local regulations.

The investigator will ensure adequate documentation of the training of research study personnel for conduct of the study, including qualifications, experience, and study role.

The investigator will be given a copy of the most current version of the cePolyTregs Investigator's Brochure and appropriate study process manuals and plans. The investigator is obligated to become familiar with these documents prior to initiation of the study.

Other investigator responsibilities relative to the IRB include, but are not limited to, the following:

- Submit to the IRB for review any advertisements that will be used to recruit subjects, as applicable
- Submit all protocol amendments, revisions of the Investigator's Brochure, or revisions of the Informed Consent to the IRB for review
- If the Sponsor notifies the investigator about SAEs reported in other studies associated with this or closely related investigational products, report that information to the IRB if required per local regulations
- Provide the IRB with any other information it requests before or during the conduct of the study
- Report to the IRB all adverse drug reactions that are serious, unexpected, and related to investigational product as per local regulations
- Maintain a file of study-related information
- Update the IRB on a minimum of a yearly basis as per local regulations

14.2 Independent Ethics Committee Approval

Before initiation of the study at a study site, the protocol, including the final version of the ICF, the subject information sheet (if applicable), and any other applicable/relevant study documentation, will be submitted to the appropriate IRB. In addition, the IRB must approve all advertising used to recruit subjects for the study prior to use. Written approval of the study documentation must be obtained and sent to the Sponsor or its designee before the study drug can be released to the investigator.

The investigator is responsible for informing the IRB of any amendments to the protocol, ICF, written information provided to subjects, and/or other procedures in accordance with local requirements. The protocol must be re-approved by the IRB upon receipt of amendments, in accordance with applicable law. The investigator must send a copy of the approval letter from the IRB to the Sponsor or its designee.

The investigator will report promptly to the IRB and the Sponsor any new information that may adversely affect the health or safety of past or current subjects or the conduct of the study, including deviations from the protocol or reports of any reportable SAEs, during and for one (1) year after study completion.

The investigator should submit written reports of clinical study status to their IRB annually or more frequently if required. A final study notification will also be forwarded to the IRB after the study is completed or in the event of premature termination of the study in accordance with the applicable regulations. After completion of the study, the investigator will provide the IRB with a report of the outcome of the study. Copies of all contacts with the IRB should be maintained in the study file. Copies of clinical study status reports (including termination) should be provided to the Sponsor.

14.3 Ethical Conduct of Study

The investigator(s) and all parties involved in this study should conduct the study in adherence to the ethical principles based on the Declaration of Helsinki, GCP, ICH guidelines, and the applicable national and local laws and regulatory requirements (referred to herein as “applicable law”).

Investigators and all sub-investigators will comply with 21 Code of Federal Regulations (CFR), Part 54, 1998 and similar conflicts of interest laws requiring documentation of financial interests or arrangements with the Sponsor, or proprietary interests in the drug under study and any other local regulatory requirements as applicable. Any required documentation must be provided prior to the investigator’s (and any sub-investigator’s) participation in the study. The investigator and sub-investigator(s) will notify the Sponsor or its designee of any change in reportable interests during the study and for 1 year following completion of the study. Study completion is defined as the date when the last subject completes all protocol-defined activities.

